5.2 ASSESSMENT OF EFFICACY

- The skin condition will be assessed by using the PASI, sPGA, and other relevant scores as described in CTP [Section 5.1](#), [Appendix 10](#), and the ISF.
- Symptoms, quality of life, and physical function will be assessed by DLQI and HAQ-DI.

Details of the efficacy assessments are listed in the [Appendix \(Section 10\)](#).

5.3 ASSESSMENT OF SAFETY

Safety will be assessed descriptively based on:

- Adverse events
- Serious adverse events
- Clinical laboratory values (haematology, clinical chemistry and urinalysis)
- Intensity of adverse events will be assessed by Rheumatology Common Toxicity Criteria (RCTC) version 2.0 (refer to ISF for details)

5.3.1 Physical examination

Complete physical examinations will be performed at visits noted in the Flow Charts. A complete physical examination will include vital sign assessment, and general appearance as well as evaluation of all relevant organ systems.

A targeted physical examination will be performed at visits noted in the Flow Charts. This includes vital sign assessment as well as an evaluation of the organ systems associated with AE(s) symptoms or laboratory abnormalities.

Clinically relevant abnormal findings will be reported as baseline conditions or AE's.

5.3.1.1 Waist circumference

Waist circumference measurements should be made around a patient's bare midriff, after the patient exhales while standing without shoes and with both feet touching and arms hanging freely. The tape should be placed perpendicular to the long axis of the body and horizontal to the floor and applied with sufficient tension to conform to the measurement surface. Waist circumference should be determined by measuring the midpoint between the lowest rib and the iliac crest.

5.3.1.2. Body weight

The scale used to capture body weight for each patient should remain consistent during the trial. In order to get comparable body weight values, it should be performed in the following way:

- Fasting (except for the screening visit);
- After the urine sampling (body weight after bladder voiding);
- Shoes and coat/jackets should be taken off; and
- Pockets should be emptied of heavy objects (i.e. keys, coins etc.)

5.3.2 Vital Signs

Vital sign evaluations will be performed at every visit as shown in the Flow Charts and includes temperature, pulse rate, systolic/diastolic blood pressure and respiratory rate. Respiratory rate, pulse rate, and blood pressure will be measured after patients have been sitting comfortably for at least five minutes. Measurement of vital signs should precede blood sampling to avoid the impact of blood sampling on the vital measurements. At dosing visits vital sign evaluations will be performed pre-dose. In addition at Visit 2 and Visit 3 vital sign evaluations will be taken at approximately 5 minutes post-dose (5 minutes after last injection) and approximately 60 minutes post-dose (60 minutes after last injection).

Patients should be closely monitored for signs and symptoms of hypersensitivity reactions for approximately 2 hours after the last injection at Visit 2 and for approximately 1 hour after the

last injection at all other visits where drug is administered. Hypersensitivity reactions should be treated according to medical standards. Pre-medications for further injections might be considered and will be agreed on between investigator and BI clinical monitor.

5.3.3 Safety laboratory parameters

For the visit schedule requiring safety laboratory sampling, see the Flow Charts. The laboratory tests listed in [Table 5.3.3: 1](#) will be performed at the central laboratory service provider. A local laboratory may be used for selected tests in exceptional cases. Patients should be fasting for at least 8 hours prior to the blood sample being taken (except screening visit).

Instructions regarding sample collection, sample handling/ processing and sample shipping are provided in the Laboratory Manual in the ISF.

Laboratory results (i.e. all safety laboratory and clinical laboratory data relevant for current clinical practice of psoriasis patients) of the patients will be available in real time to the respective investigator (via laboratory reports) and to the sponsor (via the central laboratory website) and selected abnormal laboratory alerts will be flagged to the site and sent to sponsor in real time.

Clinically relevant abnormal findings will be reported as baseline conditions or AE's. A clinically relevant value may be either inside or outside the reference range. Clinically relevant abnormal laboratory test results must be confirmed using an unscheduled visit laboratory kit and should be repeated until normalisation or stabilisation or until an alternative explanation has been found. Abnormal laboratory values will be also graded for intensity by using RCTC Version 2.0 criteria ([R13-3515](#)).

Proprietary confidential information © 2016 Boehringer Ingelheim International GmbH or one or more of its affiliated companies
 Table 5.3.3:1 Laboratory tests

Category	Test name
Haematology	Hematocrit (Hct) Hemoglobin (Hb) Glycosylated Hb (HbA1c) Red Blood Cell Count/ Erythrocytes Reticulocyte Count White Blood Cells / Leukocytes Platelet Count/ Thrombocytes
Diff. Automatic	Neutrophils (relative and absolute count) Eosinophils (relative and absolute count) Basophils (relative and absolute count) Monocytes (relative and absolute count) Lymphocytes (relative and absolute count)
Diff. Manual (if Diff Automatic is abnormal)	Neutrophils, bands (Stabs) Neutrophils, polymorphonuclear (PMN) Eosinophils Basophils Monocytes Lymphocytes
Coagulation	Activated Partial Thromboplastin Time (aPTT) Prothrombin time (INR) Fibrinogen
Enzymes	AST(GOT) ALT(GPT) Alkaline Phosphatase (AP) Creatine Kinase (CK) CK-MB, (Only if CK is elevated) Gamma-Glutamyl Transferase (GGT/γ-GT) Lactic Dehydrogenase (LDH) Amylase Lipase
Electrolytes	Calcium Sodium Potassium Chloride Bicarbonate
Substrates	Glucose BUN Uric acid Creatinine eGFR (estimated by CKD-EPI formula) Bilirubin Total Bilirubin Direct (if total is elevated) Bilirubin Indirect (if total is elevated) Troponin (Reflex when CK is elevated) Albumin C-Reactive Protein (high sensitivity) Cholesterol, total Triglycerides LDL-Cholesterol (calculated) HDL-Cholesterol HOMA-IR (V2, V9, V15, V19, EOO)
Urine Pregnancy test ¹	Human Chorionic Gonadotropin in the urine
Serum Pregnancy test ²	Human Serum Chorionic Gonadotropin

Proprietary confidential information © 2016 Boehringer Ingelheim International GmbH or one or more of its affiliated companies
 Table 5.3.3:1 Laboratory tests

Category	Test name
Hormones (screening)	TSH, (free T3 and free T4 in case of abnormal TSH results)
Autoantibodies (screening)	Rheumatoid Factor
Urinalysis (Stix)	Urine Nitrite Urine Protein Urine Glucose Urine Ketone Urobilinogen Urine Bilirubin Urine RBC/ Erythrocytes Urine WBC/ Leukocytes Urine pH
Urine-Sediment (microscopic examination, only if urine analysis abnormal)	Urine Sediment Bacteria Urine Cast in Sediment Urine Squamous Epithelial Cells Urine Sed. Crystals., Unspecified Urine Sediment RBC/ Erythrocytes Urine Sediment WBC/ Leucocytes
Urinalysis	Albumin (quantitative) Creatinine Albumin/Creatinine ratio
Infection Testing (Screening ³ V15, EOO)	Hepatitis B Surface Antigen (qualitative) Hepatitis C Antibodies (qualitative) HIV-1, and HIV-2 Antibody (qualitative) QuantiFERON®-TB ³

1. Urine pregnancy test performed on-site at all dosing visits (pre-dose) as well as EOT and EOO. (**only for female patients of childbearing potential**)
2. Serum pregnancy test at screening as well as confirmation of positive urine pregnancy test. (**only for female patients of child bearing potential at screening as well as reflex for positive urine pregnancy test**)
3. **At Screening only TB testing is required.** There is the site option to perform a PPD skin test, although this will not be provided or performed at Central Lab

5.3.4 **Electrocardiogram**

The 12-lead ECGs will be performed as scheduled in the Flow Chart(s).

ECGs will be recorded after the patients have rested for at least 5 minutes in a supine position and will always precede blood sampling. Six limb leads, as specified by Einthoven (I, II and III) and Goldberger (aVR, aVL, aVF), and six pre-cordial leads (V1–V6), according to Wilson, will be used.

ECGs will be read and evaluated by a central vendor. The study site will be informed about the results of the assessment of the ECG obtained at screening and if there are findings that would exclude the patient from study participation according to Exclusion Criterion #8.

The electronic version of the ECG is regarded as source data.

ECGs may be repeated for quality reasons and the repeat used for analysis. Additional ECGs may be collected for safety reasons. Clinically significant abnormal findings will be reported as AE's.

Information about the details of ECG collection and the parameters assessed will be provided in the ISF.

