6.0 Analysis Conventions

Definition of Baseline

The last non-missing measure collected on or before the date of the first dose of study drug injection will be used as Baseline for summary of demographics and disease characteristics, efficacy analyses, and safety analyses in each period, with the exception that:

- The last evaluation on or prior to the first dose date of risankizumab will be used for the safety analyses for Safety_ARM2 and ALL_RZB populations.
- For all vital sign assessments, only assessments prior to first dose time will be considered, since vital signs are to be assessed both pre- and post-dose in some visits.

For subjects who are randomized but do not take any study drug during the study, the last non-missing measurement collected on or before the date of randomization will be used as Baseline.

Definition of Final Observation (Applicable to Safety Analyses)

Final observation for the Part A1 is defined as:

- The last non-missing observation collected within 105 days following the last dose of study drug in Part A1, for subjects who were not dosed in Part A2.
- The last non-missing observation collected on or before the first dose date of study drug on or after Week 16 and within 105 days following the last dose of study drug in Part A1, for subjects who were dosed in Part A2. For vital sign assessments, only assessments prior to the first dose of study drug injection in Part A2 will be included in the analysis for Part A1.

Final observation for the Part A2 is defined as:

- The last non-missing observation collected within 105 days following the Week 16 dose of study drug in Part A2, for subjects who were not dosed in Part B.
- The last non-missing observation collected on or before the first dose date of Part B, or within 105 days following the last dose of study drug in Part A2, whichever comes first, for subjects who were dosed in Part B. For vital sign assessments, only assessments prior to the first dose of study drug injection in Part B will be included in the analysis for Part A2.

Final observation in Part B is defined as the last non-missing observation collected within 105 days following the last dose of study drug, and on or prior to the date first dose of retreatment with risankizumab for relapsed subjects, with the following exception:

For vital sign assessments, only assessments prior to the first dose of retreatment will be included in the analysis for Part B.

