Final observation in the retreatment period is defined as the last non-missing observation collected within 105 days after the last dose of retreatment with risankizumab.

Final observation in the entire study is defined as the last non-missing observation collected within 105 days after the last dose of study drug.

Definition of Rx Days (Days Relative to the Date of First Dose of Study Drug)

Rx days are calculated for each time point relative to the date of first dose of study drug. They are defined as the number of days between the day of the first dose of study drug and the specific time point. Rx days are negative values when the time point of interest is prior to the first study drug dose day. Rx days are positive values when the time point of interest is on or after the first study drug dose day. The day of the first dose of study drug is defined as Rx Day 1, while the day prior to the first study drug dose is defined as Rx Day –1 (there is no Rx Day 0).

For analysis in each Part (A1, A2, or B), the Rx Day is calculated relative to the first dose of study drug in the specific study Part. For analysis across Part A2 and Part B, the Rx days are calculated relative to the date of first dose of risankizumab injection in Part A2.

Definition of Analysis Windows

All time points and corresponding time windows are defined based on Rx Days.

For efficacy analyses, local tolerability, ECG, laboratory parameters, and vital sign variables, analysis windows are constructed using the following algorithm:

- Determine the nominal Rx day for each visit (e.g., Week 4 [4 weeks after Baseline visit] equals Rx Day 29).
- In order to include all post baseline data, the first post-baseline interval starts on the first day after the first dose of study drug (Rx Day 2).
- Determine the window around a specific nominal Rx day by adding or subtracting half of the interval between adjacent visits (e.g., days between Week 2 and Week 4 is 14). The threshold between adjacent visits is determined by splitting the interval evenly between the visits. If the resulting split is between Rx days, then the threshold is determined as the midpoint between the adjacent visits. If the resulting split is on an Rx day, then the threshold is determined as being between that Rx day and the Rx day prior to it (e.g., the split between Week 2 and Week 4 would be between Rx Days 22 and 23).

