- If more than one assessment is included in a time window the assessment closest to the nominal day will be used. If there are two observations equidistant to the nominal day, the one after the nominal day will be used in analyses. If more than one assessment is included on the same day, then the worst assessment on that day will be used in analyses, except those specified in Section 11.0.

The protocol specified visits and corresponding time windows used in the efficacy analyses, local tolerability, ECG, laboratory parameters, and vital sign variables, are

presented in the following Table 2, Table 3, Table 4, Table 5, Table 6, Table 7, Table 8, Table 9, Table 10, Table 11, Table 12, Table 13, Table 14, Table 15 and Table 16.

Table 2. Visit Windows for Analysis of PASI, sPGA, Local Tolerability, and Vital Signs in Part A1 (ITT_A1/PP_A1/Safety_A1 Populations)

Window Label	Target Day	Interval
Baseline	1	$\leq 1^a$
Week 4	29	[2, 43]
Week 8	57	[44, 71]
Week 12	85	[72, 99]
Week 16	113	[100, 127 ^b]

Rx Day calculated relative to first dose date of study drug. For subjects randomized but not dosed, Rx Day calculated relative to Randomization.

- a. There is no baseline for local tolerability measurements. If time is collected in vital signs, restrict to records prior to the first dose of study drug.
- b. The minimum of upper bound and first dose date of study drug on or after Week 16 (and within 105 days of last dose for safety analyses). If time is collected in vital signs, restrict to records prior to the first dose of study drug on or after Week 16.

Table 3. Visit Windows for Analysis of DLQI in Part A1 (ITT_A1/PP_A1 Populations)

Window Label	Target Day	Interval
Baseline	1	≤ 1
Week 12	85	[2, 99]
Week 16	113	[100, 127 ^a]

Rx Day calculated relative to first dose date of study drug. For subjects randomized but not dosed, Rx Day calculated relative to Randomization.

- a. The minimum of upper bound and first dose date of study drug on or after Week 16.

Table 4. Visit Windows for Analysis of Safety Laboratory Tests and ECG in Part A1 (Safety_A1 Population)

Window Label	Target Day	Interval
Baseline	1	≤ 1
Week 4	29	[2, 71]
Week 16	113	[72, 155 ^a]

Rx Day calculated relative to first dose date of study drug. For subjects randomized but not dosed, Rx Day calculated relative to Randomization.

a. The minimum of upper bound and first dose date of study drug on or after Week 16 (and within 105 days of last dose for safety analyses).

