11.5 Analysis of ECG Parameters

The ECG parameters will be assessed as scheduled in the study protocol.

Summary statistics for mean change from baseline for corrected QT interval (QTc) using Bazett (QTcB) and Fridericia (QTcF) corrections, aggregated, will be provided by analysis visits.

- Values for both QTcF and QTcB interval measurements will be categorized into the following: ≤ 450 ms, > 450 ms, > 480 ms, > 500 ms, or missing. For the scheduled visits, as well as baseline, the number and percentage of subjects within each category will be presented. Additionally, for each category, the number and percentage of subjects with a maximum QTcF interval falling into the category will be presented; a similar summary will be presented for QTcB intervals.
- For QTcF and QTcB intervals, the changes from baseline will be categorized into the following: < 30 ms, $30 \leq - < 60$ ms, ≥ 60 ms, or missing. For the scheduled visits, the number and percentage of subjects within each category will be presented. Additionally, for each category, the number and percentage of subjects with a maximum change from baseline in the QTcF interval falling into the category will be presented; a similar summary will be presented for QTcB intervals.

Analyses will be conducted in the Safety_A1 Population, the Safety_B_R Population, and the ALL_RZB Population.

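### SAP 6.0 applies a worst-of-day rule to ECGs with no exception in 11.5, so it can select a tracing that protocol 5.3.4 says is superseded by a quality repeat (minor)

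*Protocol*

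**What the plan says.** **Protocol 5.3.4 (Electrocardiogram).** The protocol distinguishes two kinds of extra tracing. For the first, "ECGs may be repeated for quality reasons and the repeat used for analysis". For the second, "Additional ECGs may be collected for safety reasons", with no rule about which tracing counts. Reading is central: "ECGs will be read and evaluated by a central vendor".

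**SAP 6.0 (Analysis Conventions).** ECG is named in the scope of the windowing rules: "For efficacy analyses, local tolerability, ECG, laboratory parameters, and vital sign variables, analysis windows are constructed using the following algorithm". Among those rules, with several assessments in a window, the one closest to the nominal day is used. For several on one day, "If more than one assessment is included on the same day, then the worst assessment on that day will be used in analyses", qualified by "except those specified in Section 11.0". The baseline definition is separate: "The last non-missing measure collected on or before the date of the first dose of study drug injection will be used as Baseline".

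**SAP 11.0.** Section 11.3.2 sets same-day rules for laboratory values (average, last or worst, depending on the table). Section 11.4.2 sets one for vital signs (average after baseline, last pre-dose value at baseline). Section 11.5 sets none for ECG. It opens with "The ECG parameters will be assessed as scheduled in the study protocol" and then lists the outputs: mean change in QTcB and QTcF, absolute categories cut at 450, 480 and 500 ms, change categories cut at 30 and 60 ms, and counts by each subject's maximum.

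**SAP 14.1.** The list of changes from the protocol does not mention ECG selection.

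**The concern.** The two documents give different answers to one question: when a tracing has been repeated the same day because its quality was poor, which QTc is analysed? The protocol points to the repeat. The SAP's default points to whichever is worse, which for QTc is naturally the longer. A programmer working from the SAP alone would apply the default, because the only permitted exceptions sit in Section 11.0 and the ECG part of it has none.

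What is at stake is the QTc safety tables. The outlier categories turn on single readings, so a few poor tracings can add subjects to them. The tables are also produced for the ALL_RZB population, which has no placebo column against which to judge a spurious count.

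**Working it through.** **1. Does the SAP's default reach ECG?** Yes. ECG is named in the scope of the windowing algorithm in 6.0, and the same-day rule is one of its steps. The exception refers to Section 11.0, and 11.5 contains no same-day or repeat rule. Its reference to the protocol concerns the assessment schedule, not the choice of tracing.

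**2. Same-day repeat.** If both tracings are in the analysis data, 6.0 takes the worse. If the superseded tracing has the longer QTc, it is analysed. Protocol 5.3.4 would use the repeat.

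**3. Repeat on a different day.** The closest-to-nominal rule applies instead. Example from SAP Table 4: the Week 4 window is Day 2 to 71 with target Day 29. With a poor tracing on Day 29 and a repeat on Day 33, the distances are 0 and 4 days, so the Day 29 tracing is used.

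**4. Size.** The documents give no QTc variability and no repeat rate, so there is no plan figure to reproduce and every input here is an assumption:

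- error SD of a valid tracing, s1 = 10 ms (also used for a single baseline tracing);
- error SD of a poor tracing, s2 = 10, 20 or 30 ms;
- independent normal errors, no true QTc change, worst = longest;
- share of ECGs repeated on the same day with the poor tracing retained, f = 1% to 5%.

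The expected excess of the longer of two readings with equal mean is √(s1² + s2²)/√(2π), with √(2π) = 2.507. Averaged over all visits it is f times that.

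| s2 (ms) | Shift at an affected visit | Average over all visits, f = 1% | f = 5% |
|---|---|---|---|
| 10 | √200/2.507 = 5.6 ms | 0.06 ms | 0.28 ms |
| 20 | √500/2.507 = 8.9 ms | 0.09 ms | 0.45 ms |
| 30 | √1000/2.507 = 12.6 ms | 0.13 ms | 0.63 ms |

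At an affected visit, the chance of a change of 30 ms or more with no true change is P(Z ≥ 30/√200) = 1.7% if the repeat is used. By simulation it is 3.1%, 10.2% or 18.3% if the longer is used (s2 = 10, 20, 30).

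Per patient, the chance of at least one such change, by simulation with a shared baseline:

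| Windows | Repeat used | Worst used, f = 1% | f = 5% |
|---|---|---|---|
| Two after baseline (Table 4, Part A1) | 3.1% | 3.1 to 3.4% | 3.2 to 4.7% |
| Nine after baseline (Table 16, ALL_RZB) | 9.7% | 9.8 to about 11% | 10.0 to about 16% |

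The top of each range needs a 30 ms SD for the poor tracing.

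**The case against.** The strongest reply is that the documents can be read together. The SAP says it elaborates the protocol's methods and nowhere revokes the repeat rule. On that reading the repeat simply stands in for the poor tracing, and worst-of-day is left for additional safety ECGs. This is sensible, and the fix below adopts it, but the SAP does not say it. What the SAP does say is a rule that covers ECG with no exception.

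Several limits stand:

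- **Data handling is unknown.** ECGs are read centrally. The documents do not say whether a superseded tracing's QTc is passed on, flagged or dropped. If it is dropped or not measurable, there is no effect.
- **The protocol wording is permissive.** It allows a repeat and its use; it does not call the first tracing rejected.
- **Worst is undefined for QTc.** The longest interval is assumed.
- **The maximum-value counts are maxima already.** They could pick up a retained poor tracing even without the same-day rule.

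A reader might also infer that changes from baseline are systematically pushed upward, because baseline takes the last value and later visits the worst. The documents do not settle this. Baseline is itself a window in Tables 4 and 16, so the same-day rule may reach it, and a repeated baseline ECG would then push changes downward.

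Nor do the documents support reading this as bias in favour of either arm, since the rule is the same in both.

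**Conclusion.** The conflict is real and worth removing, but minor. SAP 6.0, followed as written, can analyse a tracing that protocol 5.3.4 replaces with its repeat, and SAP 14.1 does not declare the departure.

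The consequence is conditional: it requires that superseded tracings stay in the analysis data with a usable QTc. Where they do, and under the assumed SDs and repeat rates, the shift is material at an affected visit, small on average over all visits, and modest in outlier counts. The claim that QTc changes and outlier counts will be inflated goes beyond the documents; they support only that they can be. The matter is confined to the safety summaries of QTc.

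**What to change.** Add to SAP 11.5, in substance:

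- an ECG superseded by a quality repeat, on the same day or a later one, is excluded and the repeat is analysed, at baseline, after baseline and in the maximum-value tables;
- the worst-of-day rule in Section 6.0 applies only to valid tracings, such as additional safety ECGs;
- worst for QTc means the longest interval.

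If the sponsor prefers to keep worst-of-day for every tracing, record that in SAP 14.1 as a departure from protocol 5.3.4.

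The cost is a few sentences and confirmation from the ECG vendor of how superseded tracings are flagged in the transferred data. No new data collection is needed.
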